7.8.2.2 Multiple Imputation Assuming Missing Not at Random

This sensitivity analysis assumes that the diary data are missing not at random (MNAR), that is, the probability that an observation is missing may depend on its underlying unobserved value.

This approach may be considered "worst-case" sensitivity analyses as it assumes that after discontinuation subjects from the dosing arms would adopt the outcome model estimated from the placebo arm. To generate missing values from this "placebo-based" imputation model, PROC MI with the MNAR statement will be used (Table 14.2.1.2.2). An example of SAS code is as follows.

PROC MI DATA=adqs NIMPUTE=100 SEED=123456789 OUT=adqs_imp ; CLASS trtp ; VAR age sex bwk twk1 twk2 twk3 twk4 twk5; FCS REG ; MNAR MODEL(bwk twk1 twk2 twk3 twk4 twk5 / MODELOBS=(trtp='PLACEBO')) ; RUN ;

where multivariate imputation is carried out by the fully conditional specification (FCS) method.

Histogram of median percent change from baseline in the frequency of IA Behaviors by imputation status in treatment and maintenance will be created for 36 mg dose and Placebo (Figure 14.2.1.2.1 – Figure 14.2.1.2.2).

7.8.2.3 Analysis of PCH Based on Data from Maintenance Period

For this sensitivity analysis, the primary analysis will be repeated using data restricted to the maintenance period only (Table 14.2.1.2.3).

7.8.3 Supplementary Analysis

A supplementary analysis will be performed based on the Per Protocol population and will be presented in Table 14.2.1.2.4.

7.8.4 Analysis Based on Adjustment of Covariates

An exploratory analysis of the primary efficacy endpoint will be performed using a randomization-based approach (Dmitrienko and Koch 2017). Separate models will be produced for the following key prognostic baseline characteristics (age [categorical and continuous] and gender [categorical]). In addition, pooled site and baseline IA adjusted to 7 days will be used as covariates (Table 14.2.1.3).

This analysis will be done by calling the following macro:

/* Linear Model with Adjustment for Covariates for Treatment period*/

%NPARCOV4(OUTCOMES = PCH_T, COVARS = gender age blsum, C=1, STRATA = center, TRTGRPS = trtp, HYPOTH = NULL, TRANSFORM = NONE, COMBINE = FIRST, DSNIN = XXXX, DSNOUT = XXXX, ALPHA = 0.05, SEED = XXXX, NREPS = 500, EXACT = NO, DETAILS = YES);

The above macro call will provide estimates of treatment effect and p-value. To obtain the 95% confidence interval, the macro will be called again specifying HYPOTH = ALT.

7.8.5 *Examination of Subgroups*

The primary efficacy variables will be summarized by subgroup to explore the heterogeneity of the treatment effect across subgroups. This analysis will be done for the following subgroups: gender (male, female), age (6-9 and 10-12), and race (White, Non-white) and baseline body weight (approximate median baseline weight: <median vs >=median). (Table 14.2.1.4.1 - Table 14.2.1.4.4).

7.8.6 Analysis of Secondary Efficacy Endpoints

The analyses of all secondary endpoints except CHQ-PF28, PSI-4-SF and SNAP-IV ADHD will be based on both the mITT and ITT population but the analysis of CHQ-PF28, PSI-4-SF and SNAP-IV ADHD will be based on the ITT population only.

7.8.6.1 Analysis of Key Secondary Efficacy Endpoint

The key secondary efficacy endpoint is the change from baseline (Visit 3) to Visit 6 in the Investigator CGI-S score.

This endpoint will be analyzed using Mixed-Effect Model for Repeated Measure (MMRM) for the mITT and ITT populations. The model includes treatment, visit, and interaction between treatment and visit as fixed factors, and baseline as covariate. The model parameters will be estimated using restricted maximum likelihood method with unstructured variance-covariance matrix and Kenward-Roger approximation to estimate denominator degrees of freedom. In case there is a convergence problem in the MMRM model with the unstructured variance covariance matrix, the first (co)variance structure which does not have convergence problem will be used for the analysis from the following ordered list: 1) Toeplitz [TOEP], 2) Autoregressive of Order 1 [AR(1)], and 3) Compound Symmetry [CS].

The least squares means of SPN-810 36 mg dose and placebo, the difference in the least squares mean (SPN-810 36 mg dose minus placebo), and the 2-sided 95% CI for the difference will be calculated (Table 14.2.2.1, Listing 16.2.2.2).

An example of SAS code is provided as follows.

```
ODS output DIFFS=DIF LSMEANS=LSMN;

PROC MIXED DATA=XXXX ;

CLASS trtp (ref='Placebo') usubjid visit;

MODEL Response = base trtp visit trtp*visit / DDFM=kr ;

REPEATED visit / SUBJECT=usubjid TYPE=UN ;

LSMEANS trtp*visit/PDIFF ALPHA=0.05;

RUN ;
```

Note: usubjid is subject ID, trtp is treatment variable, visit is the nominal study visit, and Response is respective endpoints.

In addition, the mean change from baseline by visit will be presented in Figure 14.2.4.1.

7.8.6.2 Analyses of Additional Secondary Efficacy Points

The following summaries and listings will be presented.

- 1. Investigator CGI-I score (continuous and binary) at Visits 4, 5, and 6 (Table 14.2.2.2.1 Table 2.2.2.2, Figure 14.2.3.1, and Listing 16.2.2.3)
- 2. PSI-4-SF score at visit 6 in total score and domains will be summarized in Table 14.2.2.4 (Listing 16.2.2.5.1 Listing 16.2.2.5.2).
 - a. Total Score
 - b. Parental Distress
 - c. Parent-Child Dysfunctional Interaction
 - d. Difficult Child
- 3. Caregiver CGI-I score (continuous and binary) by Visit (Table 14.2.2.5.1 Table 14.2.2.5.2, Figure 14.2.2.1, and Listing 16.2.2.3)
- 4. SNAP-IV ADHD scores at visit 6 will be summarized in Table 14.2.2.6 (Listing 16.2.2.6.1 Listing 16.2.2.6.2):
 - a. Inattention ratings
 - b. Hyperactivity/Impulsivity ratings
 - c. Oppositional Defiant Disorder
 - d. Combined Scale ratings
- 5. Percentage of responders with 50% or more reduction in the frequency of IA from baseline to treatment period (Table 14.2.2.7)
- 6. Percentage of responders with 30% or more reduction in the frequency of IA from baseline to treatment period (Table 14.2.2.8)
- 1.

Scores of CGI-I (investigator and caregiver) will be analyzed using a Mixed-Effect Model for Repeated Measure (MMRM) similar to the key secondary outcome. CGI-S will be used as baseline covariate.

Scores for CHQ-PF28, PSI-4-SF, and SNAP-IV will be analyzed using analysis of covariance (ANCOVA) on the ITT population. The model includes treatment and baseline as fixed independent covariates and Visit 6 value as a response variable. The least squares mean of each treatment group, the difference in the least squares mean (SPN-810 36 mg dose minus placebo), and the 2-sided 95% CI for the difference will be obtained.

The SAS code for the ANCOVA will be:

```
PROC MIXED DATA=XXXX ;

CLASS trtp usubjid;

MODEL Response = base trtp / DDFM=kr ;

LSMEANS trtp t/PDIFF=control ('PLACEBO') ALPHA=0.05;

RUN ;
```

Where usubjid is subject ID, trtp is treatment variable and Response is CHQ-PF28, PSI-4-SF, and SNAP-IV at Visit 6.

The Percentage of responders defined as 50% or more reduction (and 30% or more reduction) in the frequency of IA from baseline to treatment period will be analyzed using the logistic regression model with treatment as explanatory variables. Odds ratio (36 mg Dose / Placebo), and 95% CI for the odds ratio and p-value will be presented. In addition, the number and percentage of responders will be tabulated.

```
An example of SAS code follows.

ODS OUTPUT OddsRatios=or /* ODDS RATIO AND 95% CL*/

LSMeans=lsm(keep=trtpn mu) /* PROB OF RESPONDERS */ ;

PROC LOGISTIC DATA=ef1 PLOTS=none ;

CLASS siteid trtpn / PARAM=glm ;

MODEL avalc(EVENT="Yes")=trtpn;

LSMEANS trtpn / PDIFF=controll('2') ILINK ;

RUN;
```

To control family-wise error rate at 0.05 for multiple endpoints, the key secondary endpoint and additional secondary endpoints will be ordered as follows: CGI-S, investigator CGI-I, CHQ-PF28, PSI-4-SF, caregiver CGI-I, SNAP-IV ADHD, Percentage of responders with 50% or more reduction in the frequency of IA, percentage of responders with 30% or more reduction in the frequency of IA. The testing will proceed in the following order.

- 1. Test the null hypothesis H₀: There is no difference between the 36 mg dose SPN-810 and placebo will be performed with respect to CGI-S. If not rejected then the hypothesis will not be tested with respect to any additional secondary endpoint.
- If H₀ is rejected above, then proceed to test the same null hypothesis with respect to the 1st additional secondary endpoint (CGI-I). If not rejected then the hypothesis will not be tested with respect to any additional secondary endpoint after CGI-I.
- If H₀ is rejected above for CGI-I, then test of H₀ for the 2nd additional secondary endpoint (CHQ-PF28) will follow. If not rejected then the hypothesis testing will stop with respect to any subsequent additional secondary endpoint after CHQ-PF28. Otherwise, proceed

to test the same null hypothesis with respect to the 3rd additional secondary endpoint (PSI-4-SF).

The process will be repeated until all the secondary endpoints are gone through in the predefined order above in the same manner.

Subgroup (age, gender and race) analyses will be performed for the key secondary endpoint to explore the heterogeneity of the treatment effect across subgroups (Table 14.2.3.1.1-Table 14.2.3.1.3).

Supportive analyses will also be performed by summarizing the descriptive statistics for primary and secondary endpoints (Table 14.2.4.1 – Table 2.4.7).

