# 5.2.1 Clinical Global Impression (CGI) Scales

The CGI scale was developed to provide a brief, stand-alone assessment of the clinician's view of a subject's global functioning prior to and after administration of a SM (Guy 1976). Severity of illness (CGI-S) and global improvement (CGI-I) are both rated on a scale of 1 to 7 with 7 being "extremely ill" or "very much worse", respectively. Successful therapy is indicated by a lower overall score in subsequent testing. Investigators should consider their total clinical experience with children who have IA associated with ADHD and rate how severe the subject's condition is at the time.

- CGI-S will be evaluated by the Investigator at each visit on a 7-point scale with 1=Normal, 2=Borderline ill, 3=Mildly ill, 4=Moderately ill, 5=Markedly ill, 6=Severely ill, and 7=Extremely ill.
- CGI-I, relative to the condition at Baseline (Visit 1), will be evaluated by the caregiver and by the Investigator at each post-baseline visit on a 7-point scale with 1=Very much improved, 2=Much improved, 3=Minimally improved, 4=No change, 5=Minimally worse, 6=Much worse, and 7=Very much worse.

CGI-S will be assessed by the Investigator at Visit 1, Visit 3, Visit 4, Visit 5 and Visit 6. CGI-I will be assessed by the caregiver and the Investigator at Visit 4, Visit 5 and Visit 6.

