6.1 General Methodology

All statistical analyses will be conducted using SAS Version 9.4 or later on the Microsoft[®] Windows Operating System.

All tabulations of results will include summaries for the three treatment groups: SPN810 36mg, SPN810 18mg and placebo, however, statistical test will only include SPN810 36mg and placebo.

Continuous data will be summarized using n (number of subjects with non-missing observations), mean, median, standard deviation (SD), minimum value, and maximum value. Categorical data will be summarized using the frequency count and percentage (n, %) of subjects in each category. Number of subjects with non-missing values or number of subjects with missing values (e.g., Not Done) will be presented, where appropriate. Subjects with missing values will not contribute to the denominator of percentage calculations. Counts of zero in any category will be presented without percentage.

Treatment differences will be evaluated as SPN-810 dose minus placebo. Unless otherwise specified, all statistical hypothesis tests will be 2-sided with a significance level of α =0.05. All confidence interval will be calculated 2-sided from the unadjusted 5% significance level. P-values will be reported to 4 decimal places. P-values <0.0001 will be presented as "<0.0001". Similarly, p-values >0.9999 will be presented as ">0.9999"

The precision rules for the presentation of summary statistics will be:

- Sample size (n, N) and number of missing responses (if displayed) Integer
- Mean, median, percentiles, and confidence interval One additional decimal place than reported/collected
- Standard deviation Two additional decimal places than reported/collected
- Minimum, maximum Same number of decimal places as reported/collected
- Ratios two decimal places
- Percentages one decimal place generally, or two decimal places for <0.1%

The data summaries will be accompanied by individual subject data listings. All data available from diary, eCRF, and external transfer (labs) will be listed and will include relevant and pertinent subject information, e.g., treatment, center, age/gender/race, and study day. The listings will be sorted in the order of treatment group, unique subject ID, and assessment date/time and assessment name. The unique subject ID consists of 3-digit study number followed by digit site

number and digit subject number separated by hyphen (e.g.,

For each summary table, a supporting listing will be identified in the footnote.

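### If the unstructured fit of the CGI-S model fails, every listed fallback assumes one variance for Visits 4 to 6, so the Visit 6 test could run above or below its nominal 5%

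*SAP*

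**What the plan says.** SAP 7.8.6.1 analyses the change in investigator CGI-S from Visit 3 to Visit 6 by MMRM, using "restricted maximum likelihood method with unstructured variance-covariance matrix and Kenward-Roger approximation" for the denominator degrees of freedom. The example code agrees: "REPEATED visit / SUBJECT=usubjid TYPE=UN", with DDFM=kr and no EMPIRICAL option. The SAP then provides for failure: "In case there is a convergence problem in the MMRM model with the unstructured variance covariance matrix", the first structure to converge is taken in the order "1) Toeplitz [TOEP], 2) Autoregressive of Order 1 [AR(1)], and 3) Compound Symmetry [CS". No version with visit-specific variances is listed. Protocol 6.9.2 names only the unstructured matrix. The fallback appears in the SAP, which states that it supersedes the protocol's statistical methods.

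Protocol 5.2.1 fixes the visits: "CGI-S will be assessed by the Investigator at Visit 1, Visit 3, Visit 4, Visit 5 and Visit 6". The model therefore has three post-baseline visits. SAP 6.1 sets the level: "all statistical hypothesis tests will be 2-sided with a significance level of" 0.05, unless otherwise specified. SAP 7.8.6.2 carries the model over: "Scores of CGI-I (investigator and caregiver) will be analyzed using a Mixed-Effect Model for Repeated Measure (MMRM) similar to the key secondary outcome". The same section puts CGI-S first in a fixed testing order, with investigator CGI-I second and caregiver CGI-I fifth. Testing stops at the first failure.

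**The concern.** TOEP, AR(1) and CS differ in how they model correlation between visits, but each has a single variance parameter. If one of them is used, the Visit 6 standard error is built from a variance pooled over Visits 4, 5 and 6. The endpoint concerns Visit 6 alone. If CGI-S change is more variable at Visit 6 than on average, the interval is too narrow and the test too liberal. If it is less variable, the reverse holds. Kenward-Roger does not correct a wrong variance structure, and the code has no sandwich estimator.

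A rise in spread is plausible from the design. Entry requires CGI-S of at least moderately ill (4) at screening and randomization (Protocol 4.1.1). The schedule puts Visit 4 at Day 8, Visit 5 at Day 15 and Visit 6 at Day 36. At stake is the calibration of the test that opens the secondary sequence.

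**Working it through.** **Inputs from the documents.** Two-sided level 0.05 (SAP 6.1); three post-baseline visits (Protocol 5.2.1); about 121 placebo subjects of 306 randomized (Protocol 6.10); 20% attrition (SAP 3.5).

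**Assumed input.** The residual SD of CGI-S change at Visits 4, 5 and 6 is given nowhere, so a range is shown.

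**How likely is the fallback?** Unstructured with three visits has 3 × 4 / 2 = 6 covariance parameters. SAP 3.5 says about 167 subjects were randomized before the 18 mg arm closed. If they were split evenly, the two remaining arms hold about 306 − 167/3 ≈ 250. Six parameters from roughly 250 subjects should normally converge.

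**Level if the fallback is used.** Let Vc be the fitted common variance and V6 the true Visit 6 variance. With no treatment effect, the large-sample level is

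level = 2 × [1 − Φ(1.96 × √(Vc / V6))].

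Under CS, Vc is the mean of the three visit variances. For TOEP and AR(1) it was found as the large-sample likelihood limit, with visit correlations either all 0.6 or between 0.5 and 0.7.

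*Plan's own figure.* With equal variances Vc / V6 = 1, and the level is 2 × [1 − Φ(1.96)] = 5.0% under all three structures.

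*Worked example, SDs 0.9/1.0/1.1.* Vc = (0.81 + 1.00 + 1.21)/3 = 1.007 and V6 = 1.21. √(1.007/1.21) = 0.912, and 2 × [1 − Φ(1.788)] = 7.4%.

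| Assumed SD, Visits 4/5/6 | Mean variance | V6 | SE ratio (CS) | Level, TOEP/AR(1)/CS |
|---|---|---|---|---|
| 1.0/1.0/1.0 | 1.000 | 1.00 | 1.000 | 5.0% |
| 1.0/1.05/1.1 | 1.104 | 1.21 | 0.955 | 6.1% |
| 0.9/1.0/1.1 | 1.007 | 1.21 | 0.912 | 7.4% |
| 0.8/1.1/1.1 | 1.020 | 1.21 | 0.918 | 7.2-7.6% |
| 0.8/1.0/1.2 | 1.027 | 1.44 | 0.844 | 9.7-9.8% |
| 0.7/0.9/1.1 | 0.837 | 1.21 | 0.832 | 10.2-10.3% |
| 0.6/0.9/1.2 | 0.870 | 1.44 | 0.777 | 12.6-12.8% |
| 1.0/1.2/1.0 | 1.147 | 1.00 | 1.071 | 3.5-3.9% |
| 1.1/1.0/0.9 | 1.007 | 0.81 | 1.115 | 2.9% |

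**What a given level requires.** With a linear rise in SD, a level of 7% needs the Visit 6 SD to be 1.18 times that at Visit 4 (Visit 6 variance 1.17 times the average). A level of 10% needs 1.53 times (variance 1.42 times the average).

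**Simulation check.** REML fits, 121 against 129 subjects (129 is assumed), 20% monotone dropout, 1,500 runs per scenario, t reference in place of full Kenward-Roger:

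| Assumed SD, Visits 4/5/6 | Unstructured | TOEP | AR(1) | CS |
|---|---|---|---|---|
| 1.0/1.0/1.0 | 5.2% | 5.2% | 5.1% | 5.2% |
| 0.9/1.0/1.1 | 4.9% | 7.9% | 7.3% | 8.5% |
| 0.7/0.9/1.1 | 4.5% | 9.5% | 9.6% | 10.0% |
| 1.1/1.0/0.9 | 4.3% | 2.7% | 2.7% | 2.7% |

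The unstructured fit stays near 5% under the same dropout and sample size, so the departures come from the common-variance constraint. The heterogeneous structures were not simulated.

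**The case against.** The first-choice model is right, and a pre-specified, ordered fallback list is accepted practice. The trigger is remote. The inflated levels all come from SD patterns chosen to rise; CGI-S is a bounded seven-point scale with baseline already in the model, and other patterns give 5% or less. SAP 6.1 also allows a change of method before unblinding if assumptions fail, and pooled visit variances can be examined blinded. All of this stands, and it keeps the point small.

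A reader might infer that the list by itself makes the Visit 6 standard error too small. The documents do not support that, because they give no CGI-S variance by visit and the direction of the error depends on it.

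A reader might also infer that every later secondary claim is inflated. It is not: CHQ-PF28, PSI-4-SF and SNAP-IV use single-visit ANCOVA and the responder endpoints use logistic regression. A false claim on any of these still needs its own p-value below 0.05.

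Nor do the CGI-S subgroup models raise the stakes. A smaller sample makes a failed fit less remote there, but SAP 7.8.6.2 presents those analyses as exploratory and outside the testing sequence.

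The objection does not remove the defect in the fallback itself. A rule written for the case where the main model fails should not add an avoidable assumption about the one visit tested. The SAP 6.1 route relies on someone noticing and amending in time.

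**Conclusion.** The point holds as a conditional one. If the unstructured fit fails, all three listed structures impose a common variance with a model-based standard error, and the Visit 6 test is miscalibrated unless the Visit 6 variance is close to the pooled one. For an SD rise of about 20-50% from Visit 4 to Visit 6, the nominal 5% test would run at about 7-10%; for a doubling, about 13%. It is 5% with equal variances and about 3-4% in the patterns where Visit 6 varied less than average. The rise is plausible from the entry criterion and visit timing, but it is an assumption.

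The consequence reaches the CGI-S test, the two CGI-I tests if they follow the same list, and familywise error through these. Because the fallback is unlikely to be used, this is an optional improvement and not a threat to the planned analysis.

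**What to change.** In SAP 7.8.6.1, put the heterogeneous-variance structures first: TOEPH, then ARH(1), then CSH. Keep TOEP, AR(1) and CS after them as a last resort only, fitted with the EMPIRICAL option (sandwich standard errors) in place of Kenward-Roger. They should stay because they are the smallest models if the others also fail. In SAP 7.8.6.2, state that the same list applies to both CGI-I models, since similarity to the key secondary analysis leaves this open.

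The cost is one line of text and one SAS option. Each heterogeneous structure uses two more variance parameters than its homogeneous counterpart: five for TOEPH and four for ARH(1) or CSH, against six for unstructured. TOEPH is therefore only slightly simpler than the model that failed, which is why the shorter structures follow it.

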## 6.9.3 Additional Secondary Efficacy Analyses

- 1. Investigator CGI-I score at Visit 6
- 2. CHQ-28 score at Visit 6
- 3. PSI-4-SF scores at Visit 6 in:
  - a. Parental Distress
  - b. Parent-Child Dysfunctional Interaction
  - c. Difficult Child
- 4. Caregiver CGI-I score at Visit 6
- 5. SNAP-IV ADHD scores at Visit 6 in:
  - a. Inattention ratings
  - b. Hyperactivity/Impulsivity ratings
  - c. Oppositional Defiant Disorder
  - d. Combined Scale ratings
- 6. Percentage of responders with  $\geq$  50% reduction in the frequency of IA behaviors from baseline
- 7. Percentage of responders with  $\geq$  30% reduction in the frequency of IA behaviors from baseline

The other secondary endpoints will be analyzed using the ITT Population as follows:

Scores of CGI-I (investigator and caregiver) will be analyzed using a Mixed-Effect Model for Repeated Measure (MMRM) similar to the key secondary outcome.

CONFIDENTIAL Version 7.0

Scores for CHQ-PF28, PSI-4-SF, and SNAP-IV will be analyzed using the analysis of covariance method based on the ITT population. The model includes treatment and baseline as fixed independent covariates and Visit 6 value as a response variable. The least squares mean of each treatment group, the difference in the least squares mean (36 mg dose minus placebo), and the 2-sided 95% CI for the difference will be obtained.

The percentage of responders with at least 30% reduction and with at least 50% reduction in the frequency of IA behaviors per 7 days in the Treatment (Titration and Maintenance) period relative to the Baseline period will be derived analyzed using the logistic regression model with treatment as explanatory variables and baseline as covariate. Odds ratio (36 mg dose/placebo), and 95% CI for the odds ratio and p-value will be presented. In addition, the number and percentage of responders will also be tabulated.

If the null hypothesis for the primary analysis is not rejected, then no multiplicity adjustment will be done for the key secondary endpoint. If the key secondary endpoint hypothesis is rejected then, a sequential testing procedure to preserve the type I error rate at 0.05 will be conducted for the adiidtinal secondary endpoints as described below:

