1 INTRODUCTION

The purpose of this statistical analysis plan (SAP) is to ensure the credibility of the study findings by specifying the statistical approaches to the analysis of the data prior to database lock. This SAP covers the planned analyses of all data collected on the eCRFs and diary pages, and will identify handling of data issues. The statistical analysis plan presented in this document will supersede the statistical analysis methods described in the clinical protocol. Any deviations/changes from the planned analyses described in this SAP will be identified, with justification, in the appropriate section of the clinical study report. This SAP is based on the clinical study protocol 810P302, version 7.0, dated 29 March 2019 and its associated electronic case report forms (eCRF).

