3.6 Changes to Analyses Planned in the Protocol

This SAP will be updated as necessary if any changes in the protocol occur due to the expected protocol amendment impacting the SAP.

4 **DEFINITIONS AND DERIVED DATASETS**

Table 1. Terminology and Definition

| Terminology | Definition |
|----------------------------|--|
| Study Medication | SPN-810 or the matching placebo. |
| Study Day | The first dose date (Day 1) is defined as the date on which a subject took the first dose of double-blind study medication (SM), Other study days are defined relative to the Study Day 1. For visits prior to the first dose of the SM, Study Day is calculated as Visit Date – Day 1. For visits after the first dose, Study Day is calculated as Visit Date – Day 1 +1. |
| Enrolled | Subject has provided signed informed consent. |
| Randomized | Subject is assigned with the kit number for the SM. |
| Completer for the Study | Subject who completes the maintenance period (Visit 6). |
| Baseline | Unless specified otherwise, baseline is defined as the non-missing value collected most recent to and before the time of the very first dose of the SM. For example, Visit 3 CGI-S, CHQ-PF28, PSI-4-SF, and SNAP-IV are collected prior to the first dose. Their values are considered baseline for the covariate analysis. |
| Baseline Period | For subject daily IA diaries, on and prior to Visit 3 (inclusive, ≤Day 1). |
| Prior Medication | Medication collected on the Prior/Concomitant Medication CRF, with the start date prior to Study Day 1. |
| Concomitant Medication | Medication collected on the Prior/Concomitant Medication CRF, with end date on/after Study Day 1. |
| Titration Period | For subject daily IA diaries from Visit 3 through Visit 5 (v3< to \leq V5) |
| Maintenance Period | For subject daily IA diaries from Visit 5 through Visit 6 (V5< to \leq V6) |
| Treatment Period | Titration and Maintenance Periods combined |

| Terminology | Definition |
|-----------------|--|

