6.3 Adjustment for Covariates

An exploratory analysis of the primary efficacy endpoint will be performed using a randomization-based approach (Dmitrienko and Koch 2017). This analysis will include age (categorical and continuous), gender, pooled site and baseline IA adjusted to 7 days as covariates.

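### The SAP drops the protocol's baseline covariate from both responder analyses without recording why, and its example code for them needs correction

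*SAP*

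**What the plan says.** Protocol section 6.9.3 and the synopsis give the same model for the two responder endpoints (at least 50% and at least 30% reduction in IA behaviour frequency): a "logistic regression model with treatment as explanatory variables and baseline as covariate". Neither place says which baseline variable is meant.

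SAP section 7.8.6.2 gives the model as "logistic regression model with treatment as explanatory variables. Odds ratio (36 mg Dose / Placebo", with no baseline term. The example PROC LOGISTIC code agrees with that text: `trtpn` is the only term on the right of the MODEL statement.

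The SAP says it is based on protocol version 7.0, which is the version that contains the covariate. SAP section 3.6 is headed as the place for changes to protocol-planned analyses, but holds only a general statement: "This SAP will be updated as necessary if any changes in the protocol occur". The revision history, which covers the step from Version 2 to Version 2.1, does not mention the responder model either. SAP section 1 states that the SAP "will supersede the statistical analysis methods described in the clinical protocol".

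**The concern.** Two different models for the same endpoints are on record, with no reason given for the change. Because the SAP takes precedence, the treatment-only model is the operative one. Section 1 of the SAP promises that the study report will identify deviations from the SAP. Running this model would not be such a deviation, so the departure from the protocol might never be explained.

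The two responder endpoints are the last two steps of the ordered testing sequence, which is meant to hold the family-wise error rate at 0.05. At stake are power at those two steps, if the sequence reaches them, and a clean answer to anyone who asks after a borderline result why one model was reported and not the other. Adjusted and unadjusted logistic models also estimate different odds ratios, so the choice affects the reported effect as well as the p-value.

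**Working it through.** **The responder model beside the SAP's other secondary models.**

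- CGI-S (7.8.6.1): "The model includes treatment, visit, and interaction between treatment and visit as fixed factors, and baseline as covariate".
- CGI-I, both raters (7.8.6.2): "CGI-S will be used as baseline covariate".
- CHQ-PF28, PSI-4-SF and SNAP-IV (7.8.6.2): "The model includes treatment and baseline as fixed independent covariates and Visit 6 value as a response variable".
- Responders (7.8.6.2): treatment only.

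The responder analyses are the only model-based secondary analyses without a baseline term. The natural covariate already exists: SAP 6.3 lists "gender, pooled site and baseline IA adjusted to 7 days as covariates" for the exploratory analysis of the primary endpoint.

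**Size of the effect on power.** The plan states no power or responder rate for these endpoints, so there is no figure to reproduce. The arm sizes come from SAP 3.5: about 167 randomized 1:1:1, then 139 more.

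- If all 139 are allocated 2:1: 36 mg = 167/3 + 139 × 2/3 = 148; placebo = 167/3 + 139/3 = 102.
- If only the 18 mg third is re-allocated 2:1, the 36 mg share is 1/3 + (1/3)(2/3) = 5/9 and the placebo share is 4/9. Then 36 mg = 167/3 + 139 × 5/9 = 133; placebo = 167/3 + 139 × 4/9 = 117. Protocol 6.10 expects about 121 on placebo.
- With 20% fewer (× 0.8): 118 vs 82, or 106 vs 94.

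The remaining inputs are assumptions. The model is logit P(response) = a + log(2.0) × treatment + b × baseline. Baseline is standard normal, b is 0, 0.3, 0.6 or 0.9 per SD, and a is solved to give placebo response of 30%, 40% or 50%. Each setting used 10,000 simulated trials and a two-sided Wald test at 0.05. The Monte Carlo standard error is about 0.5 points per power estimate.

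| b per SD | 133 vs 117, 40% placebo: unadjusted / adjusted | 106 vs 94, 40% placebo: unadjusted / adjusted | Gain from adjusting, all sizes and rates (points) |
|---|---|---|---|
| 0 | 77.7 / 77.7% | 69.2 / 68.9% | -0.7 to +0.3 |
| 0.3 | 76.5 / 77.1% | 66.9 / 67.0% | 0.1 to 1.2 |
| 0.6 | 71.1 / 74.4% | 61.5 / 64.6% | 2.1 to 4.1 |
| 0.9 | 64.4 / 70.9% | 55.3 / 60.7% | 5.4 to 7.2 |

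Under the null (odds ratio 1, placebo 40%), rejection was 4.7-5.3% unadjusted and 4.5-5.4% adjusted, so neither model inflates the error rate. In 4,000 further trials at 133 vs 117 and 40% placebo, the two models disagreed on significance in 1%, 4%, 7% and 13% of trials as b rose from 0 to 0.9.

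A second set of assumptions (35% vs 50% responders, 122 per arm, 1,500 trials per setting) shows the change in the odds ratio. With an odds ratio per SD of baseline of 1.0, 1.5, 2.0 and 3.0, the adjusted treatment odds ratio averaged 1.86, 1.93, 2.00 and 2.23, while the unadjusted one stayed at about 1.86-1.89.

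**The example code (secondary).**

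- `PDIFF=controll` is SAS syntax for a one-sided comparison. That reading comes from the software, not from the documents. SAP 6.1 requires two-sided tests unless otherwise specified.
- The control level '2' of `trtpn` is not defined in the SAP. SAP 3.3.1 numbers placebo as Treatment 1 and 18 mg as Treatment 2. A wrong comparator is therefore possible, but not shown.
- The saved output holds the odds ratio with its CI and the response probabilities. The text also promises a p-value, whose source is not stated.
- `siteid` is in CLASS but not in the model.

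**The case against.** The best opposing argument is that the treatment-only model is coherent. Responder status is a dichotomised percent change from baseline, and the primary analysis of that same variable is a Wilcoxon test with no covariate; baseline enters only in exploratory work. CHQ-PF28, PSI-4-SF and SNAP-IV model raw Visit 6 values, where the case for a baseline term is different. The unadjusted odds ratio also matches the responder counts that the SAP tabulates. All of this stands as a reason the sponsor could give. None of it is given in the SAP.

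The power figures are also open to challenge, and fairly so. Their inputs are assumed, and any gain requires every earlier step of the sequence to succeed. The mITT population excludes baseline IA below 6 per week, which truncates the covariate, and no such scenario was run. The 20% reduction is pessimistic, because both mITT and ITT require only one valid post-randomization diary assessment. These points limit the size of the effect but do not remove the discrepancy.

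On the code, it is labelled an example, the `PDIFF` result is not among the saved output, and variable definitions are assigned to separate dataset specifications. The text already fixes 36 mg over placebo, and SAP 6.1 fixes two-sided testing and those two arms. That makes the code a secondary matter. It still does not match the text it illustrates.

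**Conclusion.** The concern holds. The SAP departs from protocol version 7.0 for both responder endpoints, in text and code, and neither SAP 3.6 nor the revision history records it. The test that would be run is valid. The cost is an unexplained departure and a possible loss of power, from about zero to roughly 7 points per test if the sequence reaches it. That range rests on an assumed conditional odds ratio of 2.0, placebo response of 30-50%, the arm sizes above and an assumed prognostic strength. Because the outcome is already relative to baseline, nothing in the documents favours the upper end. This should be corrected, but it does not threaten the trial's main conclusions.

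**What to change.** Restore baseline in the text and MODEL statement of SAP 7.8.6.2, and define it as baseline IA frequency per 7 days. The protocol says only baseline, so this definition needs to be written down. Limit the model to 36 mg and placebo, with placebo as reference, for example:

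`CLASS trtp(REF='Placebo') / PARAM=glm; MODEL avalc(EVENT='Yes') = trtp base; LSMEANS trtp / PDIFF=CONTROL('Placebo') ILINK;`

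Use the treatment label exactly as the dataset specification gives it, since the SAP's own code writes it in two ways ('Placebo' and 'PLACEBO'). State that the 36 mg/placebo odds ratio, its 95% CI and the two-sided Wald p-value all come from this one model, and save the table that holds the p-value. This replaces `controll('2')` and removes `siteid`.

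If the sponsor prefers the unadjusted model, record and justify that in SAP 3.6 and still correct the comparison, the p-value output and CLASS. Either route costs a few lines of text and code. The covariate is already collected and derived, and no extra patients are needed.
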